4.0 Proposed Analysis

The primary outcome, defined as CDI resolution at week 2, will be analyzed using the per protocol approach for all patients. Adverse events will be tabulated in each predetermined outcome.

To measure the direct medical costs, the utilization of different health care services, including pharmaceuticals, physician services, Emergency Department visits, inpatient hospitalizations, and Intensive Care Unit time will be summed for each individual patient. In order to attempt to attach a dollar value to the resource utilization, CIHI's Resource Intensity Weights (RIW) will be used. The RIW methodology derives estimated resource utilization compared to an 'average typical hospital stay', the cost of which has been calculated for the Edmonton Zone in each fiscal year from 2010/11 through 2014/15. RIW values are calculated based on the patient's Comprehensive Ambulatory Classification System (CACS) group, age and based on the patient's Case Mix Group (CMG) code, age, and comorbidity level.

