3.5 Intervention and follow up

Patients who fulfill inclusion and exclusion criteria will be screened. Once consent has been obtained, metronidazole and vancomycin will be discontinued and 2L of Golytely will be administered the night prior to FMT. Each participant will undergo a large volume enema of 720cc delivered FMT on day 1, consisting of 200g of donor stool followed by two more days of small volume FMT enema on day 2 (360 cc) and day 3 (180 cc). This constitutes as cycle 1. In the event that a colonoscopy is indicated to rule out other pathology, then the scheduled enema can be delivered at the time of colonoscopy. On day 1, the patient will also start a 7-10 day course of fidaxomicin, as long as no clinical deterioration or complication such as bowel perforation has occurred. Following the first cycle of FMT treatment and fidaxomicin, careful clinical monitoring including vitals, requirement for vasopressors (if applicable), abdominal pain and distension, stool frequency and inflammatory markers including white blood cell (WBC) and C reactive protein (CRP) will be performed daily (Figure 3.0). If the patient has improvement in clinical parameters and inflammatory markers, and has reached a plateau without further changes over 24-48 hours after the first cycle, a second cycle of enema delivery of FMT will be administered. The FMT and fidaxomicin combined cycles will continue until clinical resolution of diarrhea and/or return of inflammatory markers to baseline prior to CDI. At that point, a final FMT 180cc enema will be administered. The maximal number of cycles is 4. At any time when a patient's conditions worsens, the study team will refer patient for surgery.

Each patient will receive FMT from a single donor with multiple collections obtained over time.

Baseline characteristics including age, sex, duration and response to CDI therapy, medical history (including inflammatory bowel disease, irritable bowel syndrome, baseline bowel habit, bowel resection, chemotherapy or radiation, number of CDI in the previous 12 months) and medication use will be collected. Blood work including CBC, electrolytes, creatinine, ALT, ALP, albumin, CRP, INR, HIV, and viral hepatitis serology will be drawn at screening visit (Figure 4.0). In addition, baseline collection of blood, and stool samples will be collected and

biobanked. Repeat stool and blood samples will be collected after each cycle of treatment, and again at week 1, 2, 4 and 8 after the final FMT.

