3.6 Subject Withdraw or Termination

Subjects will be discontinued from the trial in the following situations:

- Withdrawal of consent. The subject is free to withdraw from the trial without prejudice to further medical care
- Need for urgent colectomy

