3.7 Outcome Measures

3.71 Primary Outcome

CDI resolution, defined as < 3 unformed bowel movements/ 24 hrs or a return to baseline bowel habit, 2 weeks after the last FMT treatment

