3.72 Secondary Outcomes

a) Sustained CDI resolution, defined as a lack of CDI recurrence 8 weeks after the last FMT treatment

Clinical status and biological samples will be taken to ensure that CDI has not recurred at 8 weeks

b) Adverse events

All serious adverse events will be recorded up to and including week 8 after the final FMT. A serious adverse event is any event which results in any of the following:

- Death
- Colonic perforation
- Proven infections related to FMT
- Subsequent hospitalization due to CDI within study period

c) Proportion of patients requiring colectomy

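### Section 4.0 leaves the primary analysis set ambiguous; if it means completers only, patients who fail and go to colectomy leave the denominator and the resolution rate is biased upward

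*Protocol*

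**What the plan says.** The only statement on how the primary outcome is analysed is in section 4.0: it "will be analyzed using the per protocol approach for all patients". The protocol does not define a per-protocol set or name an all-treated or intention-to-treat set. Nor does it say how to count a patient who has a colectomy, dies or withdraws before the assessment.

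Four other places bear on the point:

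- Section 3.71 defines resolution by stool count, "or a return to baseline bowel habit, 2 weeks after the last FMT treatment". It does not say that colectomy or death is a failure.
- Section 3.5 provides that, whenever a patient worsens, "the study team will refer patient for surgery".
- Section 3.6 opens with "Subjects will be discontinued from the trial in the following situations" and lists two: "Withdrawal of consent" and "Need for urgent colectomy". The patient leaves the trial, not merely the treatment.
- Section 3.72 lists the proportion needing colectomy as a separate secondary outcome. On safety it says "All serious adverse events will be recorded up to and including week 8 after the final FMT".

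Section 3.2 sets the size at 30 patients from expected patient volume and calls the study a pilot.

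**The concern.** The sentence in 4.0 can be read as naming either of two denominators. On one reading everyone is counted. On the other, only those who completed the regimen and reached the two-week assessment are counted. The protocol's own pathway sends some failures to surgery and out of the trial, so the patients on whom the two readings differ include treatment failures. Leaving them out shrinks the denominator without touching the numerator.

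Only one regimen is described, and the only comparator mentioned (section 1.0) is a historical cohort, so no concurrent arm shares the loss. At stake is the trial's main efficacy estimate: two analysts who both follow 4.0 could report different resolution rates from the same data.

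**Working it through.** **No planned figure to reproduce.** The 30 patients in section 3.2 are a feasibility number. The protocol gives no target rate, alpha, power, or expected colectomy or dropout rate. The counts below are therefore assumptions that show direction and scale; only N = 30 comes from the protocol.

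**Formulas.** Let x be the number resolved, f the failures dropped and s the resolvers dropped (for example after withdrawal of consent).

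- All patients counted: x / 30.
- Completers only: (x − s) / (30 − f − s).

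Intervals are exact (Clopper-Pearson) 95% limits.

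**Only failures dropped (s = 0).**

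| Failures dropped | x = 24 | x = 21 |
|---|---|---|
| 0 | 24/30 = 80.0% (61.4–92.3) | 21/30 = 70.0% (50.6–85.3) |
| 1 | 24/29 = 82.8% (64.2–94.2) | 21/29 = 72.4% (52.8–87.3) |
| 2 | 24/28 = 85.7% (67.3–96.0) | 21/28 = 75.0% (55.1–89.3) |
| 3 | 24/27 = 88.9% (70.8–97.6) | 21/27 = 77.8% (57.7–91.4) |

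The rise for three dropped failures is 8.9 points at x = 24 and 7.8 points at x = 21.

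**The step depends on the rate.** For the first failure dropped the rise is x/29 − x/30 = (x/30)/29. This is 2.8 points at 24/30, 2.4 at 21/30 and 2.1 at 18/30.

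**Resolvers dropped as well.** A completer set may also lose patients who resolved, which pulls the rate down. With x = 24 and f = 0, dropping 1, 2 or 3 resolvers gives 23/29 = 79.3%, 22/28 = 78.6% or 21/27 = 77.8%. To return to 80% after dropping f failures, solve (24 − s)/(30 − f − s) = 0.8. This gives 0.2s = 0.8f, so s = 4f. At an 80% rate, four lost resolvers are needed to cancel one lost failure. With three failures and three resolvers dropped the rate is still 21/24 = 87.5%.

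**When nothing shifts.** The two readings give the same rate if no patient is lost before the assessment. If the reference to all patients governs, or if a colectomy reached by the protocol's own route is not treated as a reason for exclusion, colectomy patients stay in and no upward bias arises.

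**The case against.** **A reader might infer that the sentence contradicts itself.** The text does not go that far. It can be read loosely as the analysis this protocol specifies, applied to everyone. It is ambiguous, not logically inconsistent.

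**A reader might infer that the rate will be inflated.** That needs three things together: the per-protocol wording overrides the reference to all patients; it means completers; and colectomies or deaths occur before the two-week assessment. The second is open to doubt, because a patient referred for surgery under 3.5 and discontinued under 3.6 has followed the protocol. The inflation is conditional; the ambiguity is not.

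**Analysis sets are often left to a statistical analysis plan.** One may exist but is not at hand. This would answer a complaint that detail is missing. It does not answer this one, because the protocol itself names a per-protocol primary analysis in words that fit two denominators.

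**The stakes are modest.** This is a pilot without a success threshold. The hypothesis in section 1.0 concerns the number of FMTs and length of stay, not the resolution rate. Deaths and colectomies are reported separately, and the largest shift in the table (to 88.9%) lies inside the interval around 80.0%. All of this stands and limits the severity. Separate reporting makes the loss visible but does not correct the primary rate, and a wide interval does not excuse a systematic shift.

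**A reader might also infer that 3.6 contradicts 3.72 on safety follow-up.** It does not. Section 3.6 does not say whether recording continues after discontinuation; that is silence. The colectomy count is unaffected, since the colectomy is known at that moment.

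**Conclusion.** The point holds as an ambiguity that the protocol itself fixes in place and that should be resolved. Section 4.0 does not determine which resolution rate will be reported, and nothing elsewhere settles how colectomy or death before the assessment counts.

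On a completer reading the bias from excluded failures is upward: with assumed counts of 1 to 3 dropped failures, about 3 to 9 points at a true all-patient rate of 80%, and about 2 to 8 points at 70%. Losing resolvers offsets this only weakly, although the net direction could in principle go either way. Confidence is high for the ambiguity. The size is illustrative, because the protocol gives no expected number of colectomies, deaths or withdrawals. The consequence is for the estimate and its interval; no stated test or decision turns on it.

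**What to change.** Replace the sentence in 4.0 with wording such as:

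> The primary analysis includes all enrolled patients who receive any FMT. Colectomy or death before the two-week assessment counts as not resolved. An assessment missing for any other reason, including withdrawal of consent, counts as not resolved in the primary analysis. A sensitivity analysis uses patients with an observed outcome, with colectomy and death kept as not resolved. Patients enrolled but not given FMT are reported by number and reason. A per-protocol analysis, with its set defined in advance, is supportive only.

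The line on untreated patients is needed because of the interval in section 3.5 between consent and the first FMT ("Once consent has been obtained, metronidazole and vancomycin will be discontinued"). Someone who deteriorates in that interval would otherwise not appear in the results.

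As a clarification only, 3.6 can add that discontinuation for urgent colectomy does not end the outcome and safety recording to week 8 that 3.72 already requires. This concerns data collection and sets no treatment rule.

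**Cost.** The change is wording in two sections and a few follow-up contacts; section 3.5 already allows some follow-up by phone. The reported rate may be slightly less favourable. The rule for missing assessments is deliberately conservative: if one of 24 resolvers withdrew before assessment, the primary rate would be 23/30 = 76.7%, against 23/29 = 79.3% in the sensitivity analysis. Reporting both shows how much depends on that rule.

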3.0 Methods

3.1 Study Design

Prospective, open-label, multi-center study. Sites include:

- University of Alberta Hospital, Edmonton AB

- Foothills Medical Centre, Calgary AB
- Royal Jubilee Hospital, Victoria BC

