3.2 Study Setting, Patient Recruitment and Sample Size

In-patients with severe or fulminant CDI who fulfill study criteria will be screened for potential enrollment into this study. We aim to recruit 30 patients over 2 years. As this is a pilot study with a unique patient population, the sample size is based on estimate of patient volume seen previously at all participating sites combined.

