Clinical status as well as monitoring for adverse events will be assessed daily up to 2 weeks after the final FMT while a patient is hospitalized, then weekly to week 8 after the final FMT. Patients are instructed to call as soon as there is recurrence of persistent diarrhea, and an unscheduled visit will take place if needed. Given COVID-19 pandemic, study follow-up may be conducted by phone if participants are unable to or do not want to attend study visits or if the visit is deemed non-essential by the principal investigator (PI). Due to this some of these sample collections may not be possible.

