3.73 Exploratory Outcomes

a) Costs for CDI Treatment

Direct Medical costs for CDI treatment will be obtained from administrative database to include length of hospital stay, procedures and tests performed, ICU stay and medication use.

b) Stool microbial composition analysis by metagenomics

Stool samples will be subjected to physical disruption using a bead-beating kit and microbial DNA extracted using the Qiagen QIAamp DNA stool kit and stored at -20°C. DNA will be used as input for the Illumina Nextera® XT DNA Sample Preparation Kit to construct indexed paired-end DNA libraries. The pooled and indexed library set will be denatured and sequenced on an Illumina MiSeq.

Whole-genome shotgun sequencing will be performed and taxonomic classification of reads from each library will be conducted with Kraken. The database used consisted of all bacteria, archaea, viruses, fungi, and protozoa full-length genomes from NCBI RefSeq, the human genome assembly GRCh38, and reference bacterial assemblies from the Human Microbiome Project. Read assignments were filtered with Kraken-filter using a threshold of 10%.

c) Stool Metabolomics analysis

Stool samples will be lyophilized for 24 hours using a VirTis Benchtop BTP 8ZL freeze dryer (BPS, UK). Dried samples will be weighed, and bile acids extracted using a 2:1:1 (vol) mixture of water, acetonitrile and 2-propanol in a Biospec bead beater with 1.0 mm Zirconia beads. Following centrifugation (16,000 x g, 20 minutes) the supernatant will be filtered using 0.45 µm microcentrifuge filters (Costar, Corning). Quality control (QC) samples will be prepared using equal parts of the fecal filtrates. QC samples will be used as an assay performance monitor, and as a proxy to remove features with high variation. QC samples will also be spiked with mixtures of bile acid standards (55 bile acid standards including 36 non-conjugated, 12 conjugated with taurine, seven conjugated with glycine (Steraloids, Newport, RI, USA)) and will be analyzed along with the stool samples to determine the chromatographic retention times of bile acids and to aid in metabolite identification.

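### The only unit cost named for the exploratory cost outcome, an Edmonton Zone series ending in 2014/15, matches neither two of the three sites nor the years in which stays under the current text occur

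*Protocol*

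**What the plan says.** Direct medical cost is an exploratory outcome. Section 3.73 gives the data source: "Direct Medical costs for CDI treatment will be obtained from administrative database". Section 4.0 sums services for each patient (drugs, physician services, emergency visits, admissions and intensive care) and then uses CIHI's RIWs to "attempt to attach a dollar value to the resource utilization". An RIW expresses resource use relative to an average stay, so it yields dollars only when multiplied by the cost of that stay. The one such cost that the protocol names is described by the clause "the cost of which has been calculated for the Edmonton Zone in each fiscal year from 2010/11 through 2014/15". This is a series with one value for each of five fiscal years. The protocol names no other zone, province or later year, and gives no reference year or adjustment rule.

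Section 3.1 lists three sites: the University of Alberta Hospital in Edmonton, "Foothills Medical Centre, Calgary AB" and "Royal Jubilee Hospital, Victoria BC". Section 3.2 states "We aim to recruit 30 patients over 2 years" and bases that number on "patient volume seen previously at all participating sites combined". The design is prospective. The follow-up text in section 3.5 reads "Given COVID-19 pandemic, study follow-up may be conducted by phone", and Appendix A relies on a Health Canada COVID-19 notice of 25 March 2020.

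**The concern.** The named base fits the trial in neither place nor time. One site of three is in the Edmonton Zone; of the other two, one is elsewhere in Alberta and one is in another province. The costed years end before any stay under the current text could begin.

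This goes beyond detail that a protocol may leave to a later analysis plan. The protocol itself names a base, and it is the wrong one for these patients. An analyst who followed the text literally would price stays at three sites in two provinces with one zone's older cost. What is at stake is the level of the reported dollar figures. Section 6.0 cites lower health care costs as an eventual benefit of the work, so those figures may be read outside the trial.

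**Working it through.** The protocol states no dollar value, RIW value or price index, so it has no figure of its own to reproduce. The check sets the sections side by side and then sizes the time gap under stated assumptions.

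**Place.**
- Zone of the named cost (section 4.0): Edmonton.
- Sites (section 3.1): Edmonton, Calgary, Victoria BC.
- Sites inside the zone: 1 of 3. Outside: 2 of 3.
- Patients per site and unit costs outside Edmonton: not given. The effect of place on the mean cost therefore cannot be calculated, and its direction is unknown.

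**Time.**
- Last costed year (section 4.0): 2014/15.
- Earliest year for stays under the current text: the text already relies on a notice of 25 March 2020 (Appendix A). With April-to-March fiscal years (assumed), that date falls in 2019/20.
- Gap: 2019/20 minus 2014/15 = 5 fiscal years at least.
- Recruitment is planned over 2 years (section 3.2). Counted from the notice (assumed, as no enrolment dates are given), the gap reaches 5 + 2 = 7 years.

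**Size of the time effect.** Let g be annual price growth and n the gap in years. If the 2014/15 unit cost is used unadjusted, cost at current prices is understated by 1 - 1/(1+g)^n. The range of 1% to 3% for g is an assumption.

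| Gap n | g = 1% | g = 3% |
|---|---|---|
| 5 years | 1 - 1/1.0510 = 4.9% | 1 - 1/1.1593 = 13.7% |
| 7 years | 1 - 1/1.0721 = 6.7% | 1 - 1/1.2299 = 18.7% |

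Using 2014/15 is the most favourable choice within the series; any earlier year would widen the gap. Patients enrolled under an earlier version of the protocol, if there were any, would have a shorter one.

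**Could the old years be deliberate?** Section 1.0 mentions a historical cohort, but for the number of FMTs and length of stay. Section 4.0 does not tie the cost series to that cohort, so the cohort does not explain the years.

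**The case against.** The strongest reply is that section 4.0 commits only to the RIWs. The Edmonton clause describes what has already been calculated; it does not say that this series will be applied to Calgary or Victoria patients or to later years. On this view the text merely leaves out a price source and price year, which an analysis plan could supply. The first half stands: a newer or other-zone cost is not barred, so any bias is conditional on using the named base as it is. The second half stands only in part, because the protocol does name a base, and that base does not match the trial.

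It is also fair to say that a result openly labelled in 2014/15 dollars would not be wrong for its year. The percentages above apply when the figure is read as a current cost.

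Two stronger readings are tempting, and the protocol supports neither.
- A reader might infer that a single Edmonton unit cost makes the sites incomparable. It does not: one unit cost multiplying every RIW puts all sites on the same price scale, and differences between them then reflect weighted resource use. Site-specific prices would bring price differences into the totals, so that choice is a trade-off.
- A reader might infer that the method misses how much fidaxomicin and FMT each patient received. Section 4.0 lists pharmaceuticals among the services summed, and section 3.73 includes procedures and medication use. Whether the final dollar value reflects treatment intensity cannot be settled from the protocol.

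**Conclusion.** The point holds as a minor one. The only unit cost that section 4.0 names does not cover two of the three sites, and it ends at least about five fiscal years before stays under the current text. If it were used unadjusted, the exploratory cost outcome would be off in level. For time alone, current-price cost would be understated by about 5% to 14% at the five-year gap. This rests on assumed growth of 1% to 3% a year, April-to-March fiscal years and use of the 2014/15 value. The effect of place cannot be sized or signed. The protocol plans no cost comparison or cost threshold, and the primary, secondary and safety outcomes are unaffected.

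**What to change.** In section 4.0, replace the clause on 2010/11 to 2014/15 with wording such as:

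> Each stay or visit will be valued as its RIW times a cost per weighted case for the fiscal year in which it occurs. Where that year's figure is not available, the latest available figure will be inflated to it by a named index. All costs will be expressed in one stated reference year.

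Then add one of the following, and state which was chosen:
- a common price base applied to all three sites and labelled as such, which keeps site totals on one price scale; or
- provincial figures for Alberta and British Columbia, which are closer to local prices but bring price differences into the totals.

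The cost is a unit-cost request and a little more analysis work. Which figures are available for the relevant years is not known from the protocol, hence the inflation fallback. No change to sample size, visits or the other outcomes is needed.

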5.0 Data Safety and Monitoring

An independent data safety monitoring board (DSMB) will be appointed and following the project till completion. The members of the DSMB are not involved in this trial, and will not have potential patients who might be enrolled in this study.

